In the context of a prospective, randomized study with crossover, **our specific aims are to:**

1. Determine in young adults with pre- or stage I hypertension whether ULT with 300 mg of allopurinol once daily over 4 weeks will:

1a. Lower blood pressure

Hypothesis 1: Four weeks of ULT therapy will induce a greater reduction in ambulatory blood pressure levels when compared to four weeks on placebo

Hypothesis 2: ULT will induce a greater reduction in ambulatory blood pressure levels in African Americans when compared with other races/ethnicities.

1b. Induce a change in endothelial function

Hypothesis 3: Four weeks of ULT will induce an improvement in endothelial function as indexed by flow-mediated arterial vasodilation (FMD) compared to placebo.

Hypothesis 4: ULT will induce a greater increase in FMD in African Americans when compared with other races/ethnicities.

1c. Induce a change in serum levels of high sensitivity C-reactive protein

Hypothesis 5: Four weeks of ULT will induce a greater reduction in serum levels of high sensitivity C-reactive protein (hsCRP) than placebo.

Hypothesis 6: ULT will induce a greater reduction in hsCRP in African Americans when compared with other races/ethnicities.

2. Determine if the impact of ULT on hsCRP, FMD, and blood pressure is associated with the change in serum urate achieved

Hypothesis 7: Changes in hsCRP, FMD, and blood pressure will be associated with the serum urate change observed after four weeks of ULT with allopurinol compared to placebo.

We initially aimed to recruit 112 young adults (ages 18-40 years) with pre-hypertension or JNC 7 stage I hypertension³⁷ not taking antihypertensive medication. Recruitment includes men, women, African Americans, and other races/ethnicities in equal numbers. To increase generalizability and add novelty to the research question, participants will not be required to be hyperuricemic, but to have serum urate levels ≥ 5.0

mg/dL for men and 4.0 mg/dL for women. Participants will be randomized to receive allopurinol or placebo in a four-week study with crossover. This novel translational study will generate knowledge about the mechanism by which ULT lowers blood pressure and provide evidence that can be translated into clinical practice for patients with gout or high-normal urate levels and other cardiovascular risk factors, including hypertension.

C. RESEARCH STRATEGY

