Screening visits and study entry criteria assessment. At the screening visit, the study objectives will be explained to potential participants and once interest in participating is confirmed, they will be offered an initial informed consent for the screening evaluation. Three BP measurements will be performed following the recommendations published in the report of the Joint National Committee on Hypertension³⁷ participants will sit quietly for at least five minutes with feet on the floor and arms supported at heart level, appropriate cuff sizes will be used, restrictions on alcohol and caffeine consumption for a specified time period prior to obtaining BP measurements will be imposed, and appropriate maintenance of all equipment will be performed. We will use automated BP devices for measurement of clinic BP (Omron, Bannockburn, IL, Model HEM-705CP). If the average of the second and third systolic and diastolic BP measurements taken 3 minutes apart is found to be within the pre-hypertension or stage I hypertension range (SBP \geq 120 and $<$ 160 mmHg or DBP \geq 80 and $<$ 100 mmHg) the participant will be allowed to continue with the full screening procedures to assess for study entry criteria (Table 3). Before randomization, participants will participate in a single blind run-in period lasting 2-4 weeks during which they will receive a 21-45 day supply of the daily dose of placebo.

Focused history and physical examination: Information collected will include date of birth, self-reported race/ethnicity (defined as in previous studies investigating its role in rheumatic diseases)⁷⁴, medical conditions that might preclude study participation including current or recent infections and gout, medication history (including use of aspirin, gout medications, losartan, fenofibrate), duration of hypertension, weight, and height. Gynecological history will include last menstrual date. This information will help assess the balanced allocation of participants during randomization, estimate glomerular filtration rate, establish phase of menstrual cycle for women, and identify exclusion criteria.

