Allopurinol hypersensitivity syndrome (AHS) is a very rare (occurs in less than 1 in 1000 patients), life threatening idiosyncratic reaction that is commonly preceded by rash. published prior report mentions a crude incidence rate of .69 per 1000 person years for severe AHS cutaneous reactions.⁸³ It should be noted that during the course of this study we will expose to allopurinol a total 112 (<30 participants/year) ambulatory young adults aged 18-40, with normal kidney function. The rate of AHS in younger ambulatory patients with normal kidney function has not been established but is possibly lower than in individuals with gout and other medical comorbidities. Allopurinol hypersensitivity syndrome has principally been observed in individuals that are HLAB5801 positive (primarily individuals of Han Chinese or Thai descent). As recommended in the recently released American College of Rheumatology guidelines, we will test for HLAB5801 during initial screening in individuals of Han Chinese or Thai descent.⁸⁴

5.Hypertension

Participants might be exposed to elevated blood pressure during a short period of the study. Given that adverse outcomes associated with hypertension tend to occur over time-periods measured in years and our study extends over a period of only 3-4 months, the risk of short exposure to elevated blood pressure leading to an adverse outcome is small.

To maximize the safety of the participants we have added a safety monitoring rule. When patients are seen at visits 2-5, if present with high blood pressure >160/110, first it will be rechecked 24 hrs later, if blood pressure

is still elevated, they will be excluded from the study, receive consultation by PI and/or Co-PI, and be referred to their primary care provider.

6. Hyperuricemia

Participants will not be treated for asymptomatic hyperuricemia outside the study protocol, given that they are understood not to have been diagnosed with gout for enrollment in the study.

7. Pregnancy

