This study will enroll women between the ages of 18-40 years, at which age we expect a greater majority to be fertile. If pregnancy occurs during the active treatment study period, there is a theoretical risk for the unborn as allopurinol is considered FDA class C during pregnancy. Untreated hypertension during the early pregnancy can also carry a small risk. Pregnant women will not be allowed in the study because allopurinol is classified as FDA class C during pregnancy, additionally prisoners, and institutionalized individuals will be excluded. Proper birth control methods for male and female participants will be confirmed and discussed during the screening visit.

8. Psychosocial risks

There are no obvious psychosocial risks

J. Potential Benefits

Currently, cardiovascular events caused by hypertension are the leading cause of morbidity and mortality in patients with gout and in the general population. If the addition of urate-lowering therapy to the standard therapy for hypertension reduces cardiovascular morbidity through improvement in endothelial function and inflammation in patients with hyperuricemia and those in the higher percentiles of normal serum urate concentration, this knowledge might have a significant impact on the quality of life of a large proportion of the general population.

K. Withdrawal of Participant Consent and Discontinuation of Study Drug

Participants can withdraw their consent at any time by informing the study coordinator.

This may include but is not limited to the following

- a. The subject deciding to withdraw consent for study
- b. An intolerable adverse event as judged by study investigator and/or participant
- c. The subject discontinuing acceptable birth control methods or becoming pregnant
- d. The subject enrolling in a conflicting investigational drug trial
- e. The participant BP > 160/110 between visit 2-5

If the study drug is discontinued, unless the subject withdraws consent, the subject will be followed for the full treatment period and all data will be collected as scheduled. Attempt will be made to schedule an early end of study assessment in the case of study drug discontinuation

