During the screening phase, potential participants will be determined as described in the Recruitment Plan in section 5A. Study personnel following instructions outlined in the study binder will carry out screenings. The set of screening questions will be asked prior to starting any study procedures and immediately after obtaining consent. These questions will be based on eligibility and exclusion criteria described below (see Appendix 2 for REDCap screenshots). Screening logs will be kept in electronic format and saved in a password protected file folder in the REDCap system (See Appendix 2 for REDCap screenshots) and updated as needed during recruitment.

7. Criteria

7a. Eligibility criteria

A screening visit will occur to confirm study eligibility, explain procedures, and sign an informed consent for screening. For men and women in days 1-7 of the menstrual cycle eligible for the study, randomization and the baseline visit will occur 2 weeks after the screening procedures and signing of the consent form. Women after day 7 of the menstrual cycle will be invited to return after the onset of their menses and no later than day 7 of the next cycle for standardized measurements of FMD (4 week placebo run-in ± 3 days) in the UAB Hypertension Clinic.^{85,84} Participants will be randomized following confirmation of eligibility. We anticipate an additional 10% that initially fulfill inclusion criteria will fail to randomize because their BP will be outside the study range at visit 1. In conclusion, we project the need to perform screening laboratory assessments in 236 individuals. Enrollment and participant follow-up will continue until 112 participants are enrolled. We anticipate recruiting 30 persons per year based on the following inclusion criteria.

1. Pre-hypertension or stage I hypertension, defined as the following after the mean of two clinic measurements:
 - -Systolic blood pressure (SBP) ≥ 120 and < 160 or;
 - -Diastolic blood pressure (DBP) ≥ 80 and < 100
2. Serum urate ≥ 5.0 mg/dL for men or ≥ 4.0 mg/dL for women
3. Age 18-40

7b. Exclusion criteria

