Individuals below 18 years of age will be excluded given that although hyperuricemia may affect children, it is predominately a condition of adults and gout is almost exclusively a problem of adulthood. The science proposed and the rationale for our study of this disorder in adults only is clarified in our research strategy and significance section. While prior research of this type has examined adolescents, part of the novelty of our study is to focus only on adults and given the increased risk to benefit ratio of our proposed study in children, children will not be included in this research. Prisoners and institutionalized individuals will be excluded. In individuals of Thai or Han Chinese descent that test positive for HLAB5801 will be excluded due to the high risk of allopurinol hypersensitivity.

The risks to pregnant women or an unborn baby when taking allopurinol is not fully known. For this reason, women must have a pregnancy test before the study starts and again throughout the study. Women must not become pregnant during this study. All females of childbearing potential must use an effective form of birth control during this study. Acceptable methods of birth control include hormonal control methods, intra-uterine device, a double-barrier method (diaphragm with spermicide, condom with spermicide) or abstinence.

If participants suspect that they may have become pregnant during the study, the study coordinator must contact the study PI immediately and instruct the participant to stop taking their study medication. If it is confirmed that the participant is pregnant, they will be withdrawn from the study. The study PI may want to schedule a follow up visit and may choose to follow the outcome of the pregnancy. Additionally, taking allopurinol may involve unknown risks to a nursing infant. If potential participants are breastfeeding, they are not eligible to participate in the study.

If participants suffer from very high BP $>160/110$, first it will be rechecked 24hrs later, if blood pressure is still elevated, they will be excluded from the study, receive consultation by PI and/or Co-PI, and referred to their primary care provider.

8. Informed Consent and HIPAA

8a. Overview of the informed consent process

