control and to compare its effects to placebo in 112 participants with prehypertension and stage I hypertension. [REDACTED] will be responsible for data safety and monitoring. As PIs they will complete and submit to the Project Advisory Committee monthly reports detailing the study progress and participant status, any adverse events, and any protocol deviations. Continuous, close monitoring of individual participant by the PIs will be assured throughout the study period. Events determined by the PIs to be serious, unanticipated problems involving risks, those not described in **Table 8. Adverse Events**, to the participants will be reported by the PIs to the IRB, DSMB, and the Safety Officer (via KAI) within 48 hours.

Table 8. Adverse Events – This document will be updated as needed.

Activities of Daily Living-ADL

Body Surface Area- BSA

Body System			
Cardiovascular	Mild	Moderate	Serious
Myocardial Infarction			All reported myocardial infarction will be classified as serious
Increased Blood Pressure	Systolic BP 140 - 159 mm Hg or diastolic BP 90 - 99 mm Hg; medical intervention indicated	Systolic BP \geq 160 mm Hg or diastolic BP \geq 100 mm Hg; medical intervention indicated	Life-threatening consequences (e.g., malignant hypertension, transient or permanent neurologic deficit, hypertensive crisis)
Hematology	Mild	Moderate	Serious
Anemia	13-10 Hb g/dl)	10-8 Hb g/dl	<8 Hb g/dl
Thrombocytopenia	150 000- 75 000/mm ³	<75,000 – 50,000/mm ³	<50,000 – 25,000/mm ³
Neutropenia	<LLN – 1500/mm ³	<1500-1000/mm ³	<1000-500/mm ³
Gastrointestinal	Mild	Moderate	Serious
Vomiting	1 - 2 episodes (separated by 5 minutes) in 24 hrs	3 - 5 episodes (separated by 5 minutes) in 24 hrs	\geq 6 episodes (separated by 5 minutes) in 24 hrs; tube feeding, TPN or hospitalization indicated
Diarrhea	Increase of <4 stools per day over baseline; mild increase in ostomy output compared to normal	Increase of 4 - 6 stools per day over baseline; moderate increase in ostomy output compared to normal	Increase of \geq 7 stools per day over baseline; incontinence; hospitalization indicated; serious increase in ostomy

Project 2: The Effects of Urate Lowering Therapy on Inflammation, Endothelial Function, and Blood Pressure (NIAMS: CORT)

			output compared to normal or death

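### The blood pressure entry rule joins its two ranges with 'or', so it admits people above one of its own upper limits (for example 150/105), and the >160/110 rule closes only part of the gap

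*Combined protocol and SAP*

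**What the plan says.** The same blood pressure criterion appears in three places.

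- Section 7a (Eligibility criteria) and Table 1 (Enrollment criteria) both introduce it as "Pre-hypertension or stage I hypertension, defined as the following after the mean of two clinic measurements". They then list SBP ≥120 and <160, the connector *or*, and DBP ≥80 and <100.
- Section F (screening visits and study entry criteria assessment) applies the same two ranges, also joined by *or*, to the average of the second and third readings. If they are met, "the participant will be allowed to continue with the full screening procedures to assess for study entry criteria".

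The Specific Aims name the population as young adults "with pre-hypertension or JNC 7 stage I hypertension".

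Two other provisions bear on the upper end.

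- Section 7a expects a further 10% who "will fail to randomize because their BP will be outside the study range at visit 1".
- A rule at >160/110 appears three times. Section 7b, under exclusion criteria and without naming visits, says "first it will be rechecked 24hrs later, if blood pressure is still elevated, they will be excluded from the study". Section I, item 5, says "When patients are seen at visits 2-5, if present with high blood pressure >160/110, first it will be rechecked 24 hrs later". Section K lists "The participant BP > 160/110 between visit 2-5" among the reasons for discontinuation. None of the three says whether one or both components must exceed.

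Table 8 grades increased blood pressure as Mild at SBP 140-159 or DBP 90-99. It is Moderate when SBP is at least 160 or DBP is at least "100 mm Hg; medical intervention indicated".

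**The concern.** Each range has a lower and an upper bound, and joining the ranges with *or* loosens both. That is right for the lower bounds, since one raised component is enough to be pre-hypertensive. It is wrong for the upper bounds, since stage I requires both components to be below their limits. Because the list is given as the definition of the population, a screener who follows it literally may enrol someone with DBP of 100 or more, or SBP of 160 or more, provided the other component is in range.

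What is at stake is safety at entry and agreement between the rule and the named population. Such a person would start the trial at the pressure that Table 8 calls Moderate. They would then spend 8 to 12 weeks in run-in, washout and placebo with no antihypertensive other than a stable calcium channel blocker. The within-person comparison of allopurinol with placebo is not biased, and sample size and power are unaffected.

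**Working it through.** The plan states no figure to reproduce here. The check is one of logic, followed by an illustration of size.

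**Rules compared**

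- Entry as written (7a, Table 1, section F): (120 ≤ SBP < 160) or (80 ≤ DBP < 100).
- Both limits binding: (SBP ≥ 120 or DBP ≥ 80) and SBP < 160 and DBP < 100.
- The >160/110 rule, *either* reading: SBP > 160 or DBP > 110.
- The >160/110 rule, *both* reading: SBP > 160 and DBP > 110.

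**Examples**

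| BP | Admitted as written | Both limits met | Removed, *either* | Removed, *both* |
|---|---|---|---|---|
| 130/75 | yes | yes | no | no |
| 115/85 | yes | yes | no | no |
| 145/95 | yes | yes | no | no |
| 150/105 | yes | no | no | no |
| 160/95 | yes | no | no | no |
| 165/95 | yes | no | yes | no |
| 165/105 | no | no | yes | no |

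The rule as written also rejects 165/75 and 110/102. The fault is therefore confined to people with one component in range and the other above its limit.

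**Enumeration** over whole-number pairs with SBP 90-199, DBP 50-129 and SBP > DBP:

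- SBP 120-159 with DBP 100-129: SBP 120 to 129 gives 20 + 21 + … + 29 = 245 pairs (because SBP must exceed DBP), and SBP 130 to 159 gives 30 × 30 = 900. Total 1145.
- SBP 160-199 with DBP 80-99: 40 × 20 = 800.
- Wrongly admitted: 1145 + 800 = 1945.
- Left after the *either* reading: SBP 120-159 with DBP 100-110, 40 × 11 = 440, plus SBP 160 with DBP 80-99, 20. Total 460.
- Left after the *both* reading: 1945. Every wrongly admitted pair has SBP < 160 or DBP < 100, so none can have both components above 160/110.
- Pairs admitted by the corrected rule but rejected by the current one: none.

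These are counts of possible readings, not of patients.

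**Other safeguards.** The blood pressure check before randomization in section 7a refers to the same study range, so it inherits the same gap.

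**Time without active drug** (Table 3), as run-in + washout + four placebo weeks:

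- Men, revised schedule: 2 + 2 + 4 = 8 of 12 weeks.
- Men, original schedule: 2 + 4 + 4 = 10 of 14.
- Women, revised schedule: 4 + 2 + 4 = 10 of 14.
- Women, original schedule: 4 + 4 + 4 = 12 of 16.

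**Illustration of frequency.** The documents give no distribution of screening blood pressure, so this rests on assumptions. Clinic SBP and DBP are taken as bivariate normal, rounded to whole mmHg: SBP mean 125-135 and SD 11-14, DBP mean 78-86 and SD 8-10, correlation 0.5-0.7, in 72 combinations. The quantity is the probability of being wrongly admitted divided by the probability of being admitted.

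- Exceeding one stated limit: 0.0053 to 0.106. Multiplied by 112, this is 0.6 to 11.9, or about 1 to 12 participants.
- Remaining after the *either* reading: 0.0042 to 0.097. Multiplied by 112, this is 0.5 to 10.9, or about 0 to 11 participants.

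**The case against.** The logic is hard to dispute; the case against concerns how much it matters.

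- **Adverse event definition.** Section 16 counts only events that are new or have worsened since the pre-intervention period, so a pressure of 150/105 at screening is not itself an adverse event. The Mild cell of Table 8 also says that medical intervention is indicated, and properly eligible people at 140-159 or 90-99 already fall there. This stands as a limit: the point is only that the person enters at the Moderate threshold. It also cuts the other way. The next grade in Table 8 is life-threatening consequences, so grading gives little warning for that person and the ambiguous >160/110 rule becomes the main numeric safeguard.
- **On-study tolerance.** The plan accepts DBP up to 110 during the study, and section I argues that elevated pressure over 3-4 months carries small risk. Someone correctly enrolled at 150/95 could drift to 150/108 and continue. The corrected entry rule does not change that. It does stop people starting there, which the plan's own limits evidently intend.
- **Exposure.** The 8 to 12 weeks apply to every participant, and nobody is taken off treatment to enter. This is true; the weeks describe the exposure of a wrongly admitted person and are not an extra burden created by the rule.
- **Frequency.** The range is wide and assumed. Its highest values all come from a DBP mean of 86 with SD 10. Without rounding, the median left after the *either* reading is about 2.2%, or 2 to 3 of 112. A single reading per person also ignores the repeat checks.
- **Practice.** Clinicians may have applied both limits, and the REDCap eligibility logic is not visible in the screenshots. Whether anyone was wrongly enrolled cannot be known from the documents.

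These points lower the seriousness. None makes the written rule agree with its own limits.

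**Conclusion.** The concern holds. As written in all three places, the criterion admits people whose systolic or diastolic pressure is at or above the plan's own upper limit. No other provision fully closes the gap: 150/105 and 160/95 pass on every reading, and 165/95 is caught only if >160/110 means either component. These conclusions rest on the text alone.

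How often it would happen cannot be taken from the documents. The figure of about 1 to 12 of 112, or about 0 to 11 after the *either* reading, depends on the assumed blood pressure distributions and on screeners applying the rule literally. This is a defect in eligibility wording with a safety aspect, and it is worth correcting. It does not threaten the treatment comparison.

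**What to change.** In section 7a, Table 1 and section F, restate the criterion as: (SBP ≥120 or DBP ≥80) and SBP <160 and DBP <100. This keeps 130/75, 115/85 and 145/95, rejects 150/105, 160/95 and 165/95, and admits nobody whom the current rule rejects. Simply changing *or* to *and* would be wrong, because it would exclude people with one raised and one normal component, such as 130/75.

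In section I item 5, section K and section 7b, state that >160/110 means SBP >160 or DBP >110. Confirm that the REDCap eligibility flag follows the corrected rule.

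The cost is six wording changes, one check of the form logic and possibly a few more screen failures.
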